2. BACKGROUND

Rationale. This exploratory mechanistic target engagement study will assess the effect of brief DA supplementation on dopamine availability, nigro-striatal functional connectivity and mobility in a sample of older adults with parkinsonian signs.

The study will screen elderly people for the presence of slow walking (not explained by peripheral or musculoskeletal reasons) and/or other parkinsonian signs. Subjects will be contacted for participation in this study from an existing database in the lab. However, if enough subjects can't be recruited from this database then subjects will be recruited through external sources, such as a flyer posting, online registries, and the University of Michigan Movement Disorders Clinic and other physicians. These subjects will be screened using the telephone screening script, and after this screening they will be brought into the lab to screen for the presence of slow walking and/or other parkinsonian signs. If the clinical assessment does not show evidence for these parkinsonian signs then the person will be excluded from the C-L Dopa and imaging portions of the study (see study outline below).

[figure not shown]
We will record eligibility, adherence, and tolerability to 1-week supplementation (3 days of carbidopa monotherapy and 7 ± 3 days of C-L Dopa at one tablet PO TID for three days followed by an increase to 1.5 tablets PO TID the next day for the next 4 days (± 3 days)), and the effects of C-L Dopa on mechanistic imaging measures of DA sensorimotor functional connectivity and on clinical mobility functions. This translational aim will provide preliminary information about the targeted modifiability of the DA system in non-resilient elderly with parkinsonian signs.

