3. RESEARCH PLAN

General Overview:

Study design: Open-label study. An outline of the study is shown in Figure 1. After obtaining informed consent, subjects (max n=60) will undergo a screening exam to assess for parkinsonian signs, including slow walking speed. Elderly subjects without evidence of parkinsonian signs will be excluded from the C-L dopa and imaging portions of the study. Eligible subjects with evidence of parkinsonism (max n=20) will then complete a motor, including gait, cognitive test battery, [¹⁸F]FDG PET scan (optional), and 3T brain MRI (optional) prior to starting the C-L Dopa treatment portion of the study (Refer to Table 1 and Table 3). Subjects will be pre-treated with carbidopa monotherapy 25 mg TID PO for 3 days. Prior to initiating C-L Dopa 25/100 one tablet PO TID for three days subjects will repeat a limited clinical test battery on day 4. Subjects will then increase to 1.5 tablets PO TID on day 7 (i.e., day 4 of C-L Dopa treatment) for the next 4 days (± 3 days). Carbidopa monotherapy will be given to prevent possible side-effects of nausea and participants will stay on 25 mg carbidopa PO TID for the duration of the treatment period of the study. Participants are given the option to be clinically observed in the lab for their first dosage of C-L Dopa. This optional observation would be 60-120 min in length where the participant will take their first dose of C-L Dopa and be monitored by study personnel. After the week-long (± 3 days) C-L Dopa 25/100 trial the complete test battery will be completed. An (optional) [¹¹C]PE2I dopamine PET scan will be performed for assessment of overall nigrostriatal degeneration. This target engagement study will allow for biomechanistic assessment of hypothesized changes in the DA sensorimotor network and will allow us to correlate the C-L Dopa mechanistic effects on DA sensorimotor connectivity changes before/after target engagement as assessed with multimodal graph analytical network methods using optional post-treatment [¹⁸F]FDG and MRI of key relevant circuits related to DA. Dopamine PE2I PET scan will be used for post hoc covariate effects.

Figure 1. Study outline.

Subjects:

Eligibility: Non-resilient elderly non-PD subjects (F/M, age 60 yrs or older) with evidence of mild parkinsonian signs (MPS, slow gait (< 1m/s)). The UPDRS motor component (part III) will be used to assess for evidence of parkinsonian signs, including bradykinesia, tremor, rigidity, and gait disturbances.

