Inclusion:

- 1) Age 60 or older (M/F)
- 2) Evidence of mild parkinsonian signs (incl. MPS, slow gait (< 1m/s))

Exclusion:

- 1) Evidence of prior established diagnosis and/or treatment for PD¹³.
- 2) Presence of clinically significant degenerative joint disease and/or neuropathy interfering with proper assessment of the motor UPDRS exam.
- 3) Presence of significant dementia.
- 4) History of stroke with residual clinical deficit interfering with walking.
- 5) For optional MR imaging only: Participants in whom magnetic resonance imaging (MRI) is contraindicated including, but not limited to, those with a pacemaker, presence of metallic fragments near the eyes or spinal cord, or cochlear implant.
- 6) For optional brain imaging only: Severe claustrophobia precluding neuroimaging procedures.
- 7) Participants that have been on monoamine oxidase inhibitors (MAOIs) within 2 weeks prior to starting study.
- 8) Inability to stand or walk without an assistive device
- 9) Hypersensitivity to the carbidopa, levodopa, and tablet components.
- 10) History of myocardial infarction (MI) with residual arterial, nodal or ventricular arrhythmia
- 11) History of peptic ulcer
- 12) Chronic wide angle glaucoma

- 13) Narrow angle glaucoma
- 14) Major psychotic disorder
- 15) Severe cardiovascular or pulmonary disease, bronchial asthma, renal, hepatic or endocrine disease
- 16) Subjects on dopamine D2 receptor antagonists, dopamine depleting agents, and metoclopramide.
- 18) Any other medical history determined by investigators to preclude safe participation.

Study Timeline:

The study will be performed over 2 years with anticipated net recruitment and completion of half of the subjects per year. A milestone of success will be recruitment of 5 subjects who have completed the CL Dopa treatment by the end of year 1. The last 2 months will be used for data analysis and report writing.

Dissemination plan:

Study findings will be published in peer-reviewed journals and presented at scientific meetings.

Design: Within-subject study design using after-before difference measures.

Sample size: This is an exploratory pilot study to generate sample size effects for future larger scale studies, with a net study completion goal of 20 treated subjects.

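### The entry criteria count gait below 1 m/s whatever its cause, although the rationale sets aside peripheral and musculoskeletal slowing

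*Combined protocol and SAP*

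**What the plan says.** Four places in the combined protocol and SAP bear on who may enter on slow gait.

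- **Section 2, Background (Rationale).** Screening is for "slow walking (not explained by peripheral or musculoskeletal reasons) and/or other parkinsonian signs". The cause of slow walking is part of the definition, and slow walking is one of two routes in.
- **Section 3, Subjects, Inclusion 2.** The criterion is "Evidence of mild parkinsonian signs (incl. MPS, slow gait (< 1m/s" with no condition on cause. The Eligibility paragraph just before it uses the same speed threshold, also without a condition. It adds that part III of the UPDRS will be used to "assess for evidence of parkinsonian signs, including bradykinesia, tremor, rigidity, and gait disturbances".
- **Exclusion 2.** "Presence of clinically significant degenerative joint disease and/or neuropathy interfering with proper assessment of the motor UPDRS exam". This is the only criterion that names joint disease or neuropathy.
- **Exclusion 4, for comparison.** "History of stroke with residual clinical deficit interfering with walking". Here the test is the effect on walking.

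Two further exclusions act as partial filters: Exclusion 8, "Inability to stand or walk without an assistive device", and Exclusion 15, "Severe cardiovascular or pulmonary disease, bronchial asthma, renal, hepatic or endocrine disease". Exclusion 18 lets investigators exclude for other medical history, but only on grounds of safety.

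**The concern.** Whether the UPDRS motor exam can be done properly and why a person walks slowly are separate questions. Someone with mild knee or hip disease, or a mild sensory neuropathy, may walk at 0.9 m/s for that reason and still have an adequate motor exam. With no other parkinsonian sign, that person is outside the population in the Background, yet meets Inclusion 2 and need not meet any exclusion.

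Exploratory H1 is that one week of treatment improves walking by raising dopamine, and gait parameters head the list of primary outcomes. The stated purpose of the sample is to supply effect sizes for larger studies. With at most 20 treated subjects and no control group, a few participants from outside the intended population can move the mean change. Nothing in the criteria or in Table 3 asks for the judged cause of slow gait to be recorded, so the analysis could not later separate these people from the rest.

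**Working it through.** **Step 1: follow one person through the text.** Take a person aged 60 or over who walks below 1 m/s because of mild joint disease, with no bradykinesia, rigidity or tremor, who walks unaided and has no severe comorbidity.

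| Rule | Result |
|---|---|
| Background, slow-walking route | Not met: the cause is musculoskeletal |
| Background, other parkinsonian signs | Not met |
| Inclusion 2 | Met: speed is below 1 m/s |
| Exclusion 2 | Applies only if the disease interferes with the UPDRS motor exam |
| Exclusion 4 | Does not apply: no stroke |
| Exclusion 8 | Does not apply: walks unaided |
| Exclusion 15 | Does not apply: no severe disease |
| Exclusion 18 | Does not apply: no safety concern |

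The Background and the criteria therefore disagree about this person, unless an examiner reads Exclusion 2 broadly enough to reach the gait part of the exam. If the same person also has rigidity or bradykinesia, the two agree, because the Background's second route is open.

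This takes slow gait alone to be enough under Inclusion 2. The wording there is not fully clear, but the Background's and/or supports that reading, and so does the Study design paragraph, which lists slow walking speed among the parkinsonian signs.

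**Step 2: what the plan's figures allow.** The plan gives a completion goal of 20 treated subjects and a cap of 20 eligible subjects. It gives no alpha, power, effect size or standard deviation, so there is no power calculation to reproduce. It also gives neither the share of peripherally slow entrants nor their response. What follows is for scale only.

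**Step 3: mean effect.** Let q be the share of treated subjects who are slow for peripheral reasons, and r their response as a fraction of the response in the intended population. Both are assumed. The observed mean effect, relative to the intended one, is 1 - q(1 - r).

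| q | of 20 | r = 0 | r = 0.5 | r = 1 |
|---|---|---|---|---|
| 0.2 | 4 | 0.80 | 0.90 | 1.00 |
| 0.4 | 8 | 0.60 | 0.80 | 1.00 |

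**Step 4: worst case, r = 0.** At an unchanged standard deviation, a later trial sized on the diluted effect would need 1/(1 - q)² times the subjects: 1/0.64 = 1.56 at q = 0.2 and 1/0.36 = 2.78 at q = 0.4.

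Mixing responders and non-responders also widens the spread of change scores, so the standardised effect becomes d_eff = (1 - q)d / √(1 + q(1 - q)d²). Take d = 0.66, the value at which a paired t-test with n = 20 has 80% power at an assumed two-sided alpha of 0.05.

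- q = 0.2: d_eff = 0.528/√1.0697 = 0.51. Power is 58%, and the sample-size factor is (0.66/0.511)² = 1.67.
- q = 0.4: d_eff = 0.396/√1.1045 = 0.38. Power is 36%, and the factor is (0.66/0.377)² = 3.07.

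At q = 0.2, power falls from 57% to 38% for d = 0.5 and from 92% to 73% for d = 0.8. At r = 1 none of this loss occurs.

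**The case against.** The strongest objection is that the protocol does not treat peripherally impaired people as non-responders. The Specific Aim section says that dopamine neurotransmission weakens the harm that peripheral impairment does to walking speed, and hypothesises that it drives resilience to such impairment. A reader might infer from the criteria gap that the walking effect will be diluted. The documents do not support that as a fact: zero response is an assumption without a source. This objection stands, and it reduces the dilution to a possibility. It does not remove the mismatch. Having a peripheral impairment is not the same as having slow gait that is accounted for by one, and the Background itself draws that line.

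Second, a reader might infer that the rationale demands non-peripheral slow walking of everyone. It does not: its and/or opens a second route, and the condition on cause attaches only to the first. This also stands and confines the gap to people with no other parkinsonian sign.

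Third, Exclusion 2 reaches further than a quick reading suggests. Part III assesses gait, so joint disease or neuropathy that accounts for slow gait can reasonably be judged to spoil that part of the exam. Exclusions 8 and 15 also help. This stands in part: what remains is mainly milder disease, left to each examiner's reading.

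Fourth, a reader might conclude that a null result could not be interpreted at all. That goes too far. The optional PE2I PET scan is planned for post hoc covariate effects, and the Impact paragraph foresees exploring moderators of response. These help only in part, because the scan is optional and the cause of slow gait is not recorded.

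**Conclusion.** The point holds as an inconsistency between the rationale and the operative criteria, with a limited reach. The Background conditions slow walking on its cause, the Eligibility paragraph and Inclusion 2 do not, and the exclusions do not fully make up the difference. The people affected are mainly those with milder peripheral or musculoskeletal slowing who enter on slow gait alone. As written, the target population differs according to which section is read.

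The effect on the results cannot be computed from the documents. Under assumed shares of 0.2 and 0.4, the mean walking effect would be 80% and 60% of the intended one if these people did not respond at all, and 100% if they responded equally. The sample-size factors in the working (1.56 to 1.67, and 2.78 to 3.07) illustrate the zero-response end only. They matter only if a later trial enrols the narrower population. A trial that kept the same criteria would properly be sized on the pilot's average effect.

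**What to change.** Reconcile the Background with the Eligibility paragraph and Inclusion 2 by using the Background's own wording in both: gait below 1 m/s counts under "slow walking (not explained by peripheral or musculoskeletal reasons) and/or other parkinsonian signs". This also settles whether slow gait alone is enough for entry.

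Add one item to the Day 0 clinical and neurological assessment: the examiner's judged cause of slow gait (for example peripheral or musculoskeletal, not so explained, or mixed). The change in walking can then be described by cause.

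Leave Exclusion 2 without a general test of interference with walking. That would go beyond the Background and could remove people with mixed causes, whom the resilience hypothesis concerns. If the sponsor does want people whose slow gait is peripheral in origin, the Background should be changed instead, and the recorded cause becomes more useful still.

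The cost is a wording change in two places and one recorded item at an examination already scheduled. The downside is a somewhat lower pass rate among the up to 60 screened.

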	Pre-Rx (Day 0) Baseline	Day 1-3	Day 4	Day 4-6	Day 7-10(±3)	Day 10 (±3)
Informed Consent	✓					
Demographic Information	✓					
Inclusion/Exclusion Criteria	✓					
Clinical & Neurological Assessment	✓					✓
Optional: Saliva sample	✓					
MDS-UPDRS	✓		✓			✓

Mini-BESTest (optional: APDM Sensored)	✓		✓			✓
Regular timed walking single & dual-task Optional: Zeno Walkways Single, Dual, and challenged gait Task	✓		✓			✓
Optional: APDM Mobility assessments	✓		✓			✓
Optional: Oculovestibular	✓					✓
Pegboard	✓		✓			✓
Finger tapping	✓		✓			✓
Foot tapping	✓		✓			✓
Optional: Reaction Time Test/ Optional: React Stick Test	✓					✓
Optional: Four Square Step Test	✓					✓
Optional: Maximum Step Length Test	✓					✓
Activity questionnaire	✓					✓
Balance confidence/fear of falling: The Activities-specific Balance Confidence (ABC)	✓					✓
Optional: New-FOGQ	✓					✓
Optional: Short FES-I	✓					✓
Sensonics UPSIT	✓					optional: ✓
Optional: Eyetech OCAT	✓					✓
MoCA	✓		✓			✓
Optional: MMSE	✓					✓
DKEFS-STROOP	✓		✓			✓
DKEFS-TMT	✓		✓			✓
Optional: CVLT	✓					✓
Information processing	✓		✓			✓
General Feeling Questionnaire	✓					✓
Apathy Evaluation Scale	✓					✓
Geriatric depression scale	✓					✓
Spielberger anxiety scale	✓					✓
Optional: BPRS	✓					✓
Epworth Sleepiness Scale	✓					✓

Mayo Sleep Questionnaire (22)	✓					✓
FSS	✓					✓
Optional: Insomnia Questionnaire	✓					✓
Optional: Somnolence VAS	✓		✓			✓
Snellin Test	✓					✓
Optional: Rabin	✓					✓
Adverse event assessment	✓	✓	✓	✓	✓	✓
Optional MRI	✓					✓
Optional FDG PET	✓					✓
Optional PE2I PET (will occur only 1 time)	✓					✓
Optional DEXA	✓					
Optional 90-120 minute observation (post medication) after first intake				✓		
Carbidopa Monotherapy 25 mg TID PO		✓	✓	✓	✓	✓
C-L Dopa 25/100 1 tablet PO TID			✓	✓		
C-L Dopa 25/100 1.5 tablet PO TID					✓	✓
Compliance Monitoring Phone Call		✓			✓	
Optional: Actigraphy		✓	✓	✓	✓	✓

Analysis:

Statistical analysis: We anticipate that 90% of eligible subjects will complete the 1-week C-L Dopa supplementation; the effect of C-L Dopa administration on brain connectivity and mobility measures will be tested using a repeated measures design.

Comments: This exploratory open label pilot study will investigate the feasibility for future clinical trials of C-L Dopa therapy in non-resilient elderly with parkinsonian signs.

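### The completion goal of 20 equals the cap of 20 eligible subjects, yet the plan expects only 90% of them to complete, which gives about 18

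*Combined protocol and SAP*

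**What the plan says.** All the figures are in section 3 (Research Plan) of the combined protocol and SAP.

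- **Screening, under Study design:** "subjects (max n=60) will undergo a screening exam to assess for parkinsonian signs". This number applies before eligibility is known.
- **Entry, under Study design:** "Eligible subjects with evidence of parkinsonism (max n=20) will then complete a motor" and cognitive battery, with optional imaging, before treatment starts. The cap of 20 is therefore attached to eligible subjects at baseline.
- **Goal, under Sample size:** the target is worded as "with a net study completion goal of 20 treated subjects", and the paragraph presents the trial as an exploratory pilot meant to inform the sizing of later, larger ones.
- **Pace, under Study Timeline:** "anticipated net recruitment and completion of half of the subjects per year", over two years.
- **Completion rate, under Statistical analysis:** "We anticipate that 90% of eligible subjects will complete the 1-week C-L Dopa supplementation".

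The text available for review contains no replacement rule and no allowance for enrolling more than 20 eligible subjects. It gives no alpha, power, effect size or standard deviation.

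**The concern.** The cap and the completion rate share a denominator, eligible subjects, so they can be multiplied directly. The product is below the stated goal. A goal equal to the maximum intake leaves no room for the 10% loss that the plan itself expects.

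The reader is left with two open questions: whether 18 or 20 before-after pairs are planned, and whether at most 20 or about 23 subjects may enter treatment. In a feasibility pilot, the numbers entering and completing are results in their own right, and later trials will be sized from them. Each should be stated once and consistently.

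**Working it through.** **Inputs**

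- Cap on eligible subjects: 20 (Study design)
- Completion rate among eligible subjects: 0.90 (Statistical analysis)
- Goal for treated completers: 20 (Sample size)

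**1. Can the goal be reproduced?** Expected completers = cap × rate = 20 × 0.90 = 18.0. The goal of 20 is not reproduced. With at most 20 entering, it requires 20/20 = 100% completion.

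**2. How likely is full completion?** If subjects complete independently with probability 0.90, P(20 of 20) = 0.90^20 = 0.12.

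**3. How many entrants would 20 completers need?** Entrants = 20/0.90 = 22.2, rounded up to 23. The binomial probabilities use the same independence assumption.

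| Entrants | Expected completers | P(at least 20 complete) |
|---|---|---|
| 20 | 18.0 | 0.12 |
| 22 | 19.8 | 0.62 |
| 23 | 20.7 | 0.81 |

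An entry of 23 exceeds the stated cap by 3. The 90% is a round forecast, so the choice between 22 and 23 should not be pressed. Both are above 20.

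**4. What does the gap cost in precision?** The 95% confidence interval half-width for a mean within-subject change, in SD units of the change, is t(0.975, n−1)/√n.

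- n = 18: 0.497 SD
- n = 20: 0.468 SD
- Ratio: 0.497/0.468 = 1.06, about 6% wider

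**5. Illustration only.** The plan sets no alpha or power. Assuming a paired t-test, two-sided alpha 0.05 and 80% power, the detectable mean change is 0.70 SD with 18 pairs and 0.66 SD with 20. The plan specifies a repeated measures design, with some tests also given on day 4, so this simplifies the eventual analysis.

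**The case against.** The strongest reply is that the three figures are different kinds of statement: a ceiling, an aspiration and a forecast. A goal set at the ceiling with a forecast below it is optimistic but not impossible, and the Sample size paragraph never says that 20 completers are expected. The word net usually means after losses. If the 20 in Study design is that same net figure, the conflict disappears and only unclear wording remains.

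Two further points can be made. The 90% refers to completing the levodopa week and the goal to completing the study, so the two counts could differ. The study outline figure, which is not visible in the text reviewed, might also carry numbers.

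Part of this stands. The completers-only reading is possible and cannot be ruled out. But Study design attaches the cap to eligible subjects before treatment and does not say that it counts completers. If it does, the number who may enter is stated nowhere. The two completion counts should nearly coincide, because the Timeline paragraph above Table 3 has the final tests done while subjects are still taking the drug. The screening limit of 60 does not help, since it applies before eligibility. A goal may be aspirational, but it is the only sample size the plan gives and should agree with the plan's own forecast.

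**Conclusion.** The concern holds, as a minor inconsistency. Read as written, the cap and the anticipated rate give 18 expected completers against a goal of 20, a shortfall of 2.

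This rests on taking the cap at its face meaning, as a limit on eligible subjects entering baseline testing. The 12% chance of reaching the goal also assumes independent completion at exactly 90%. Confidence is moderate, because the completers-only reading remains open.

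The practical effect is slight. No hypothesis test is powered on 20, no decision in the plan depends on it, and the loss of precision is about 6%. This is a correction worth making if the document is revised, not a reason to hold the study.

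**What to change.** Restate the Sample size paragraph so that entry and completion appear as separate figures: up to 20 eligible subjects entered, with about 18 expected to complete at the anticipated 90% rate.

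If the cap was meant to count completers, say so under Study design instead and give the number who may enter, which the 90% rate puts at about 23. The sponsor knows which was intended; the text does not settle it.

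The first option costs one sentence and adds no enrolment, visits or analyses. Its only price is a stated completer figure lower by 2. The second is also a short clarification, but it makes explicit that more than 20 subjects may enter treatment.

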Impact: Data collected in the proposed study may help identify a novel therapeutic approach to gait slowing in non-resilient elderly with parkinsonian signs, which could have large public health ramifications given the prevalence and serious morbidity of non-specific parkinsonism in the elderly. This project also will elucidate the neurobiology of gait slowing at structural and functional levels of analysis, increasing our understanding of the interplay between these aging-associated processes and the brain network changes underlying late life mobility disorders. Exploring patient-level moderators of response to C-L Dopa may provide useful information to guide differential therapeutics and develop personalized medicine for non-resilient elderly.

Testing:

Table 1: Main components of the Test Battery, including detailed gait and balance assessments

Test	Primary outcome parameter	Admin. Time
Motor: MDS-UPDRS ²	PIGD UPDRS sub-score	15 min
Gait: Timed walking tests (single & dual task gait). Optional: Electronic gait assessments using mats (Zeno Walkways, Protokinetics) and/or sensors (APDM) under single and dual test conditions and challenged gait.	Assessment of standard spatiotemporal gait parameters & variability measures	2 min
Dynamic balance: Mini-BESTest ³ , with optional APDM sensors	Total Mini-BESTest score	15 min
Balance confidence/fear of falling: The Activities-specific Balance Confidence (ABC) scale ⁴	Total ABC score	5 min
		Total: 35 min

Primary Outcome variables:

- (a) Biomechanical gait and postural parameters
- (b) Cognition
- (c) Optional: Brain network connectivity analysis of DA networks using multi-modal MRI and metabolic connectivity based on FDG PET.

Study Treatment:

Carbidopa Monotherapy: Due to the small risk of nausea and vomiting from taking C-L Dopa, all subjects will be pretreated with carbidopa 25 mg orally (PO) three times a day (TID) monotherapy for 3 days prior to starting C-L Dopa.

C-L Dopa administration: A low dose (25/100 1 tablet orally (PO) three times a day (TID) of C-L Dopa immediate release will be used for the first three days of C-L Dopa treatment then if no side-effects will be increased on day 4 of the C-L Dopa treatment to 1.5 pills TID PO. All participants will continue to take carbidopa 25 mg TID PO for the whole duration of the treatment period.

Drug Supplies: Formulation, Preparation and Dispensing

Carbidopa Monotherapy:

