Slices (n = 160) will be reconstructed to 1mm isotropic resolution. This sequence maximizes contrast among grey matter, white matter and CSF and provides high resolution delineation of cortical and subcortical structures. Other standard sequences include FLAIR, DTI, resting state functional connectivity MRI, or other relevant series. The brain MRI scan can be performed on the same day as the clinical assessment or on a separate day prior to starting study drug treatment.

PET imaging (optional): All PET data will be acquired at the University of Michigan PET facility on a Siemens BioGraph TruePoint Model 1094 PET/CT scanner, which produces 109 slices, has an axial field-of-view of 22.0 cm with slice thickness of 2.027 mm, and intrinsic image resolution 4.2 mm full-width at half maximum (FWHM). Image reconstruction for both tracers will be done with fully 3D-iterative OSEM, using 4 iterations, 16 subsets, and post-reconstruction files of 3.0 mm FWHM, yielding images of ~5.0 FWHM. One low-dosage CT scan (130 kVp, 30 eff mAs, 6 x 3mm collimation, pitch =1, rotation time =0.6 second) of the head will be performed prior to each brain PET scan for attenuation correction purposes. "As low as reasonably achievable" (ALARA) techniques will be utilized to minimize subject radiation exposure. Subjects will be studied supine, with eyes and ears unoccluded, resting quietly in a dimly lit room. [¹⁸F]FDG and [¹¹C]PE2I PET ligands are non-approved radiopharmaceutical that will be used in accordance with Food and Drug Administration regulations (21 CFR 361.1). All tracers are prepared following standard synthesis routines at the University of Michigan PET Chemistry and Cyclotron facilities.

Daily life activity levels (optional): Overall activity levels during medication therapy will also be assessed. Subjects will be asked to wear an accelerometer based actigraphy device (Actigraph or ActivPAL) for the duration of the carbidopa monotherapy and carbidopa-levodopa mechanistic study.

Compliance Monitoring Phone Call: A compliance phone call will be performed by a research staff member during the 7±3 C-L Dopa medication stage.

Timeline: Refer to table 3 for timeline and test details. Day 0 may be completed over multiple visits. Once all tasks listed under Day 0 are completed Day 1 will start. Day 9(±3) tasks will be performed while participant is still taking C-L Dopa and may require multiple visits.

Table 3. Detailed components, test protocol, and timeline

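### The Timeline text puts the final on-treatment tests at Day 9 (±3), while Table 3 and the stated exposure give Day 10 (±3); read literally, it allows testing on Day 6, before the dose increase

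*Combined protocol and SAP*

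**What the plan says.** All places cited are in the Combined protocol and SAP.

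- **Section 3, Timeline paragraph:** "Day 9(±3) tasks will be performed while participant is still taking C-L Dopa and may require multiple visits". The same paragraph opens with "Refer to table 3 for timeline and test details".
- **Section 3, Table 3:** there is no Day 9 column. The full battery, the repeat MRI and the repeat FDG PET are ticked under Day 10 (±3). In that column the 1.5-tablet row is ticked and the 1-tablet row is blank.
- **Section 2, Background:** the course is "7 ± 3 days of C-L Dopa at one tablet PO TID for three days". The higher dose of 1.5 tablets then runs for a further 4 days, with the same tolerance of 3 days either way.
- **Section 3, General Overview:** a limited battery is done on Day 4 before C-L Dopa begins. The dose step is fixed by day: "Subjects will then increase to 1.5 tablets PO TID on day 7". On the final battery: "After the week-long (± 3 days) C-L Dopa 25/100 trial the complete test battery will be completed".
- **Section 3, Study Treatment:** the step up is conditional, "then if no side-effects will be increased on day 4 of the C-L Dopa treatment to 1.5 pills TID PO".
- **Section 3, Design:** "Within-subject study design using after-before difference measures".

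**The concern.** Two current statements give different days for the same visit. A Day 6 visit complies with the Timeline text and deviates from Table 3; a Day 13 visit does the reverse.

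The lower end matters more, because Day 6 is the day before the dose increase. The Timeline sentence has one safeguard, that the participant is still on C-L Dopa, and a Day 6 visit satisfies it.

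The Day 4 battery precedes the first C-L Dopa dose. Apart from optional activity monitoring, the final assessment is therefore the only efficacy measurement scheduled on levodopa. A participant tested on Day 6 would contribute an after-before difference that reflects less treatment than the plan's own minimum, with no later visit to replace it. The study aims for 20 treated participants and is meant to supply effect sizes for larger studies, so each difference should reflect the intended treatment.

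**Working it through.** **Inputs.** First C-L Dopa day = 4 and dose increase on Day 7 (General Overview, Table 3). Total C-L Dopa = 7 ± 3 days, so 4 to 10 (Background). Days at 1.5 tablets = 4 ± 3, so 1 to 7 (Background, General Overview).

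**Reproducing Table 3, route 1 (total exposure).** Test day = 4 + C-L Dopa days − 1, counting the test day.
- 4 days: 4 + 4 − 1 = Day 7
- 7 days: 4 + 7 − 1 = Day 10
- 10 days: 4 + 10 − 1 = Day 13

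**Route 2 (by dose step).** Test day = 4 + 3 days at 1 tablet + days at 1.5 tablets − 1.
- 1 day: 4 + 3 + 1 − 1 = Day 7
- 4 days: 4 + 3 + 4 − 1 = Day 10
- 7 days: 4 + 3 + 7 − 1 = Day 13

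Both routes give Day 10 (±3), exactly as in Table 3. Neither gives Day 9.

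**The two windows compared.** C-L Dopa days = test day − 4 + 1. Days at 1.5 tablets = test day − 7 + 1, or 0 before Day 7.

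| Source | Test day | C-L Dopa days | Days at 1.5 tablets |
|---|---|---|---|
| Timeline, earliest | 6 | 3 | 0 |
| Timeline, centre | 9 | 6 | 3 |
| Timeline, latest | 12 | 9 | 6 |
| Table 3, earliest | 7 | 4 | 1 |
| Table 3, centre | 10 | 7 | 4 |
| Table 3, latest | 13 | 10 | 7 |

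Only Day 6 falls below the minimums of 4 and 1. Days 7 to 12 lie within both windows.

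**Counting convention.** If the test day is not counted, Day 6 follows only 6 − 4 = 2 completed days, and a full 7 completed days would put the test on 4 + 7 = Day 11. That is further from Day 9, so the convention does not rescue the Timeline figure.

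**Day 7 itself.** A test on the morning of Day 7, before the first 1.5-tablet dose, follows 3 days at 3 × 100 = 300 mg of levodopa, or 900 mg. That is the same as at the end of Day 6. Changing 9 to 10 does not close this gap, which is why the fix adds a rule about the dose step.

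**The case against.** The strongest reply is that the rest of the plan already rules out Day 6. The Timeline paragraph sends the reader to Table 3. Table 3 shows only the 1.5-tablet dose at the final visit. The General Overview places the complete battery after a course of at least 4 days. On that reading Day 9 is a slip and Table 3 governs. This largely stands and is why the point is minor. It does not make the sentence correct: the sentence is a scheduling statement in current text, and no stated rule resolves the conflict beyond the general reference to the table.

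A reader might infer four stronger points, none of which the documents support:

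- **That the ±3 days is itself an error because cumulative levodopa varies threefold.** With full dosing counted on the test day, Day 7 gives 900 + 450 = 1350 mg and Day 13 gives 900 + 7 × 450 = 4050 mg; 4050 / 1350 = 3. But this follows from a window the plan chose openly, the scheduled daily dose is constant at 450 mg from Day 7, and the plan does not use cumulative dose as an exposure measure.
- **That motor tests and scans will be 6 days apart.** Six days is only the width of the window (13 − 7). Nothing suggests such spacing is expected, and the scans are optional.
- **That dose and treatment day will be unknown.** The plan records adherence and tolerability, has pharmacy accountability and includes compliance calls. Visit dates would give the treatment day. Some text was also removed before review, so silence proves little.
- **That baseline to final is the only available contrast.** The Day 4 battery after carbidopa alone allows another, and the analysis is described as repeated measures. What remains true is that the final battery is the only one on levodopa.

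It is also fair to say that, once the day is corrected, the extra rule adds only the order of events on Day 7. That is a small gain, at almost no cost.

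**Conclusion.** The concern holds as a minor internal inconsistency. The Timeline figure of Day 9 (±3) is wrong against the plan's own exposure, which gives Day 10 (±3) by two routes and agrees with Table 3. Its practical reach is one day in seven: a Day 6 assessment would have 3 C-L Dopa days and none at 1.5 tablets, against minimums of 4 and 1.

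This assumes that C-L Dopa starts on Day 4 as scheduled, that the test day counts as a treatment day, and that the increase takes place on Day 7. If the increase is withheld for side-effects, the 1.5-tablet minimum cannot apply, but the 4-day minimum still does. That Day 9 is a slip is an inference; the documents do not say so. Whether any participant would be tested on Day 6, and what that would do to gait or imaging results, cannot be derived from them.

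**What to change.** 1. In the Timeline paragraph, replace Day 9 (±3) with Day 10 (±3).
2. Add one sentence: no final motor test or post-treatment scan (repeat MRI, FDG PET) is done before the Day 7 dose step has been taken or, if the increase is withheld for side-effects, before Day 7. The second clause lets participants held at 1 tablet complete the study.

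Cost: one number and one sentence. Day 6 is lost from the Timeline window and possibly part or all of Day 7, while Day 13 is gained. No visit or procedure is added, the ±3 days stays, and nobody is removed from the analysis.

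Optional, and not a correction of an error: record the daily dose and C-L Dopa day at each final test and scan and list them beside the after-before differences, and schedule near Day 10 or later where practical.
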